Name Modified Date

CS14.0 Are you using UPMC facilities and/or UPMC patients during the conduct of your research study?

* Yes

If Yes, upload completed Research Fiscal Review Form:

Name Modified Date
<FRIAR IOPI.docx> 9/2/2015 11:44 AM

View: CS15.0 - CS15.0.1(a)

Cover Sheet Section

CS15.0 Indicate the sites where research activities will be performed and/or private information will be obtained.

Choose all sites that apply and/or use **Other** to include sites not listed:

Sites:
UPMC

University of Pittsburgh

Campus:

There are no items to display

List university owned off-campus research sites if applicable:

UPMC

Sites:

UPMC Presbyterian

UPMC Montefiore

UPMC Shadyside

UPMC Cancer Network Sites:

Site

There are no items to display

If you selected **School, International or Other**, list the sites:

***For research being conducted at non Pitt or UPMC sites, upload a site permission letter granting the researcher permission to conduct their research at each external site:**

Name Modified Date

CS15.1 **Have you, [name] , verified that all members of the research team have the appropriate expertise, credentials, and if applicable, hospital privileges to perform those research procedures that are their responsibility as outlined in the IRB protocol?**

* Yes

CS15.2 **Describe the availability of resources and the adequacy of the facilities to conduct this study:**

* The UPMC Dept. of Otolaryngology treats individuals with qualifying diagnoses for this research at both UPMC Shadyside and UPMC Presbyterian/Montefiore. Each clinical office has board certified

clinicians in their respective fields that are extremely qualified in treating patients with swallowing difficulties. Additionally, clinicians have extensive research experience. Each clinic has both physicians and speech language pathologists who will be able to identify, educate, enroll and implement the minimal amount of research procedures necessary for the conduct of this research during clinical appointments of potential subjects. The study team has access to protected servers for data security and information protection whenever data is generated, collected, or stored.

View: CS16.0

Cover Sheet Section

CS16.0 **Special Research Subject Populations:**

Categories
None

View: CS17.0

Cover Sheet Section

CS17.0 **Does your research involve the experimental use of any type of human stem cell?**

* No

View: Clinical Trial Study

NIH Definition of a Clinical Trial

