1.1 **Objective: What is the overall purpose of this research study?** (Limit response to 1-2 sentences.)

To determine the effectiveness of the IOPI in the management of treatment induced dysphagia following chemoradiation for oral pharyngeal cancer.

1.2 **Specific Aims: List the goals of the proposed study (e.g., describe the relevant hypotheses**

or the specific problems or issues that will be addressed by the study).

To compare standard exercise therapy plus IOPI to standard exercise alone to determine if recovery is enhanced and to determine if rate of recovery is accelerated.

1.3 Background: Briefly describe previous findings or observations that provide the background leading to this proposal.

The IOPI device is one of the most commonly used measurement techniques available to measure tongue strength and endurance. Some research studies have indicated that it can be used to investigate influences of age, gender and medical condition on tongue strength and speech.

1.4 Significance: Why is it important that this research be conducted? What gaps in existing information or knowledge is this research intended to fill?

This is a pilot study designed to look at any enhancement the IOPI device might have, when paired with standard therapy for dysphagia following chemoradiation.

View: 2.01

Section 2 - Research and Design Methods

2.1 Does this research study involve the use or evaluation of a drug, biological, or nutritional (e.g., herbal or dietary) supplement?

* No

2.1.1 Does this research study involve an evaluation of the safety and/or effectiveness of one or more marketed nutritional (e.g., herbal or dietary) supplements for the diagnosis, prevention, mitigation or treatment of a specific disease or condition or symptoms characteristic of a specific disease or condition?

*

2.1.1.1 List each of the marketed nutritional supplements being evaluated in this research study. Specify for each supplement the corresponding IND number or attach FDA correspondence specifying that an IND is not required.

Marketed nutritional supplement

IND number

There are no items to display

Upload FDA correspondence specifying that an IND is not required, if applicable:

Name Modified Date Version

View: 2.02

Section 2 - Research Design and Methods

2.2 **Will this research use or evaluate the safety and/or effectiveness of one or more devices?**

* Yes

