2.2.1 **Does this research study involve an evaluation of the safety and/or effectiveness of one or more devices not currently approved by the FDA for general marketing?**

* No

If YES, describe your **plan to prevent unauthorized use of the investigational device**:

2.2.1.1 **List each of the unapproved devices being evaluated in this research study.**

Specify for each listed device the corresponding Investigational Device Exemption (IDE) number or provide a justification for why you feel that this device and its use, as proposed in this research study constitute a non-significant risk (i.e., to include potential failure of the device) to the research subjects:

Unapproved device IDE # Non-significant risk justification

There are no items to display

View: 2.02.2 - Involve evaluation of saftey/effectiveness of one or more devices FDA-approved

Section 2 - Research Design and Methods

2.2.2 **Does this research study involve the use or evaluation of the safety and/or effectiveness of one or more devices approved by the FDA for general marketing?**

* Yes

2.2.2.1 **Does this research study involve an evaluation of one or more FDA-approved devices**

for a clinical indication, subject population, and/or operational parameter that is not specified in the current FDA-approved product labeling for that device (i.e., for an “off-label” indication)?

* No

2.2.2.1.1 List each of the devices being evaluated for an “off-label” indication. Specify for each listed device the corresponding Investigational Device Exemption (IDE) number for this device/research study; or provide a justification for why you feel that this device and its “off-label” use, as proposed in this research study (i.e., to include potential failure of the device) constitute a non-significant risk to the involved research subjects.

*

Device IDE # Non-significant risk justification

There are no items to display

View: 2.03 - Summarize general classification

Section 2 - Research Design and Methods

2.3 Summarize the general classification (e.g., descriptive, experimental) and methodological design (e.g., observational, cross-sectional, longitudinal, randomized, open-label single-blind, double-blind, placebo-controlled, active treatment controlled, parallel arm, cross-over arm) of the proposed research study, as applicable.

Randomized, observational, longitudinal, descriptive, crossover

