Once enrolled through written informed consent, research participants will be assigned to either "standard therapy" or to "standard therapy with IOPI" treatment group by a clinical investigator. This assignment will be in an alternating fashion based on date of enrollment. IOPI treatment consists of 10 repetitions of the IOPI exercises, three times a day on three days per week for 8 weeks. It will take 30 minutes to train the subject on how to do the exercises and record them and that it takes 5-10 minutes to complete 30 repetitions of the exercise. Subjects will be completing a diary related to their exercise regimen.

Subjects will undergo a standard of care modified barium swallow study by clinical staff prior to the onset of therapy to obtain baseline measurements of airway protection and oropharyngeal kinematic function. They will also be asked to complete a Visual Analog Scale (VAS) to rate their dysphagia prior to initiation of therapy, therapy by marking an "X" on a 100mm line indicating their perception of the severity of their dysphagia (0 = least severe, 100 = most severe). They will also be asked to complete a dietary assessment tool/questionnaire consisting of 10 items (EAT-10). Tongue isometric pressure generation (strength) will be measured with the IOPI. This requires the subject to press a small plastic air-filled bulb between the tongue and hard palate, which transfers isometric pressure on the IOPI. The Functional Oral Intake Scale (FOIS) will be used by the clinician to rate current level of oral intake. Finally subjects will be weighed.

Approximately 8 weeks after the initiation of therapy ("standard" or "standard w/ IOPI") individuals will be asked to complete the VAS and the EAT-10, and the clinician will repeat the FOIS and weigh the subjects, once again at their 8-week standard of care clinical follow up visit. 8 weeks is the usual standard of care follow up visit. A modified barium swallow (MBS) test will also be performed as part of standard of care at about the 8 week time point (after therapy). Finally isometric pressure (tongue strength) will be measured at this point.

At 8 weeks, individuals who were assigned to the "standard therapy only" group, who still require swallowing therapy, will be asked if they would like to add the IOPI to their therapy

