We will perform t-tests to compare the dependent variable values from each measure (penetration-aspiration scores, pharyngeal retention scores, swallow kinematic measures, tongue pressure scores, EAT-10 scores, VAS scores, and patient weight. We may also perform ANOVAs and post hoc analyses to determine the main effect of treatment condition on the dependent variables, and to determine the presence of any interaction effects, and single subject analyses using the C statistic, to determine individual effect sizes for individual participants. Analyses will be designed to compare performance at the following time points:

1. between groups comparisons at time 1 (start of treatment) and at 2 (end of treatment) to evaluate differences between groups at the start and end of 8 weeks of therapy.
2. within groups comparisons between time 1 and 2 (standard therapy vs. standard therapy + IOPI) to evaluate the magnitude of differences from beginning to end of therapy.
3. within group comparison (standard treatment crossover only) at time 1 and time 3 (8 weeks after crossover of standard treatment subjects into standard therapy + IOPI) to evaluate the magnitude of differences from beginning of therapy to end of second phase of therapy (combined standard therapy, with crossover to standard + IOPI).

View: 2.19 - 2.19.6

Section 2 - Research Design and Methods

2.19 Will this research be conducted in (a) a foreign country and/or (b) at a site (e.g., Navajo Nation) where the cultural background of the subject population differs substantially from that of Pittsburgh and its surrounding communities?

* No

Note that copies of training records, licenses, certificates should be maintained in the study regulatory binder and are subject to audit by the Research Conduct and Compliance Office (RCCO).

In addition, individuals planning to conduct human subject research outside the United States must complete an optional module on the CITI training website: International Studies. [Click here](#) to access the instruction sheet for accessing optional CITI modules.

2.19.1 Address the following for each of the foreign/culturally different sites where this research will be conducted:

- Name of site
- Name of authorized individual (e.g., IRB Chair) from the local IRB or other human subject protections entity that is responsible for the review and approval of the project; upload approval letter with an English translation, if applicable

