Upload recruitment letters/scripts/text:

Name Modified Date

Research Registry

List the IRB approval number and title for each registry source:

4.2 Provide a detailed description of your recruitment methods, including identifying and initiating contact with participants:

Potential research subjects will be initially contacted at the University of Pittsburgh Medical Center Department of Otolaryngology outpatient clinic while there for routine clinical evaluation. They will be approached by their clinician who may also be an investigator of this research project. The investigator or clinician, who will be trained in all research procedures, will present information about this research study. If the potential research subject is interested, the informed consent process will be initiated.

Note: Questions jump from 4.2 to 4.6 as questions 4.3-4.5 have been removed and the information is now captured in 4.1

View: 4.06

Section 4 - Subject Recruitment and Informed Consent Procedures

4.6 Are you requesting a waiver to document informed consent for any or all participants, for any or all procedures? (e.g., a verbal or computerized consent script will be used, but the subjects will not be required to sign a written informed consent document.

This is not a waiver to obtain consent.

* No

4.6.1 Identify the specific research procedures and/or the specific subject populations for which you are requesting a waiver of the requirement to obtain a signed consent form.

If not all, identify the specific procedures and/or subject populations for which you are requesting a waiver:

4.6.2 Indicate which of the following regulatory criteria is applicable to your request for a waiver of the requirement to obtain a signed consent form.

45 CFR 46.117(c)(1) That the only record linking the subject and the research would be the consent document and the principal risk would be potential harm resulting from a breach of confidentiality. Each subject will be asked whether the subject wants documentation linking the subject with the research, and the subject's wishes will govern; or

45 CFR 46.117(c)(2) That the research presents no more than minimal risk of harm to subjects and involves no procedures for which written consent is normally required outside of the research context.

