- process for child assent and parental permission
 - continued participation if a child subject turns 18 during participation
- process for obtaining proxy consent and assent for decisionally impaired subjects
 - continued participation if subject regains capacity to consent

The potential research subject will be approached by their clinician who may also be an investigator on this research study. The clinician or investigator will provide information about participation, including the purpose of the study, the potential risks and benefits of study participation, and their rights as a research subject. The clinician or the investigator will go through the informed consent document with the potential research subject prior to enrollment. The investigator and/or clinician will answer any questions that the potential research subject may have about this research study. Consent will ultimately be obtained by the clinician or one of the investigators on this project as approved by the IRB.

4.13 Are you requesting an exception to either IRB policy related to the informed consent process?

- For studies involving a drug, device or surgical procedures, a *listed physician* investigator is required to obtain the written informed consent unless an exception to this policy has been approved by the IRB
- For all other studies, a *listed* investigator is required to obtain consent (Note: In order to request an exception to this policy, the study must be minimal risk)

* Yes

If Yes, provide a justification and describe the qualifications of the individual who will obtain consent:

We are requesting an exception to the IRB policy requiring a "listed physician investigator" to obtain written informed consent from participants.

The reason for this request is that additional clinicians in the Department of Otolaryngology will have the required knowledge to complete the informed consent process. Currently, there are 5 Speech Language Pathologists (currently not listed as co-investigators) that will be directly involved in the care of the participants. These individuals will be assisting with the swallowing testing as well as instructing the subjects in the proper therapy techniques and proper use of the IOPI device. With proper instruction on the details of the protocol, these additional 5 SLPs who are assisting directly with the care of these individuals will be adequately qualified to answer questions related to this research.

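### Section 2.3 calls the trial randomized, but section 2.6 assigns arms by alternation on enrolment date, so the next arm can be foreseen before a patient is approached

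*Combined protocol and SAP*

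**What the plan says.** Section 2.3 describes the design as "Randomized, observational, longitudinal, descriptive, crossover".

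Section 2.6 is the only place that says how arms are allocated. After written consent, participants are assigned to a "treatment group by a clinical investigator", and "This assignment will be in an alternating fashion based on date of enrollment".

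On recruitment, section 4.2 says of potential subjects: "They will be approached by their clinician who may also be an investigator of this research project". Section 4.12 adds: "Consent will ultimately be obtained by the clinician or one of the investigators on this project as approved by the IRB". Section 4.13 asks that five speech language pathologists who are not listed as co-investigators may also take consent. The same therapists will teach patients to use the IOPI.

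CS15.0 lists three UPMC hospitals. CS15.2 says the department "treats individuals with qualifying diagnoses for this research at both UPMC Shadyside and UPMC Presbyterian/Montefiore".

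The objective in section 1.1 is "To determine the effectiveness of the IOPI in the management of treatment induced dysphagia". Section 2.18 plans t-tests, including "between groups comparisons at time 1 (start of treatment) and at 2 (end of treatment"). Sections 3.10 and 3.11 plan 50 patients per arm, 100 in all.

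**The concern.** Randomization requires a chance sequence, and it protects against selection only if recruiters cannot see the next arm. Alternation provides neither. Once the previous assignment is known, the next one is fixed. That assignment comes after consent does not help, because the arm can already be known when someone decides whether to approach a patient.

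A recruiter who foresees the arm may, even unintentionally, enrol or pass over patients according to how well they are expected to do. The arms then differ in prognosis before treatment starts, and the week-8 comparison mixes that difference with any effect of the IOPI. Section 2.18 commits to no adjusted analysis, and its ANOVAs are optional. Adjustment would in any case not remove selection on unmeasured factors such as motivation, which plausibly matters in an eight-week exercise programme recorded by diary.

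The rule is also incomplete. Section 2.6 does not say whether alternation runs by patient or by calendar date, or whether there is one sequence or one per hospital.

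**Working it through.** **Text.** Section 2.3 states a chance allocation and section 2.6 a deterministic one. No section of the available text gives a random sequence, an independent allocator, envelopes or a central service. The uploaded flow chart and consent form are not in the text, but section 2.6.1 says the flow chart does not replace the description in 2.6.

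**Predictability.** Take one alternating sequence of 100 patients. The first arm is a coin toss for the guesser and the other 99 are certain, so the expected share guessed correctly is (0.5 + 99)/100 = 99.5%. Under simple randomization it is 50%.

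**Possible size of bias.** The plan has no figure to reproduce. The only input from the documents is 50 per arm. The rest are assumptions:

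- *q*: share of patients steered away from an arm and not enrolled, 10-20% (5% as a low case)
- *r*: correlation of the recruiter's view of prognosis with outcome, 0.3-0.5
- *s*: 2 if poor-prognosis patients are kept out of one arm and good-prognosis patients out of the other, 1 if only one of these happens
- *k*: share of enrolments at which the next arm is known

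Bias in SD units = s × k × r × m, where m is the mean of a standard normal variable after its lowest fraction q is removed: m = φ(z_q)/(1 − q). For q = 0.10, m = 0.1755/0.90 = 0.195. For q = 0.20, m = 0.2800/0.80 = 0.350.

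The standard error of a difference in means is √(2/50) = 0.20 SD. The rejection rate of a two-sided 5% test under a true null is 1 − Φ(1.96 − bias/0.20) + Φ(−1.96 − bias/0.20).

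| Scenario | q = 0.10, r = 0.3 | q = 0.20, r = 0.5 |
|---|---|---|
| Both directions, arm always known (s = 2, k = 1) | 2 × 0.3 × 0.195 = 0.117 SD; 9.0% | 2 × 0.5 × 0.350 = 0.350 SD; 41.7% |
| One direction, always known (s = 1, k = 1) | 0.058 SD; 6.0% | 0.175 SD; 14.1% |
| Both directions, known at one half (s = 2, k = 1/2) | 0.058 SD; 6.0% | 0.175 SD; 14.1% |
| Both directions, known at one third (s = 2, k = 1/3) | 0.039 SD; 5.4% | 0.117 SD; 9.0% |

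With only 5% steered and the arm always known, the rate is 6.2-8.4% (both directions) or 5.3-5.8% (one direction) for r = 0.3-0.5.

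If steered patients are deferred and come back under the other arm, the lowest fraction q all end in one arm and the highest fraction q all in the other. The bias is then 4 × φ(z_q) × r: 4 × 0.1755 × 0.3 = 0.21 SD, and 4 × 0.2800 × 0.5 = 0.56 SD. Simulation of 400,000 enrolments agrees.

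**The case against.** The strongest reply is that this is a pilot sized on expected recruitment (section 3.12), with no stated alpha and no single primary outcome. Correcting the label would then be essential, and changing the allocation method only desirable. There is something in this, and the fix below does allow alternation to be kept under an honest description. But the pilot rationale explains the sample size, not the allocation. The protocol still states an effectiveness objective and plans between-group tests.

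Several features reduce the risk:

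- Standard-arm patients who still need therapy are offered the IOPI at 8 weeks, which weakens the motive to steer.
- The person taking consent need not be the person assigning, although the therapists in section 4.13 also teach the IOPI and so may learn recent arms.
- With several hospitals, a recruiter may not know the last assignment elsewhere. CS15.0 lists three hospitals, while CS15.2 reads more like two locations, so both one third and one half are shown above.

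These points stand as limits on the size of the bias. They do not supply a random sequence.

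The baseline comparison in section 2.18 might reveal an imbalance, but it is a weak safeguard. By the same arithmetic, a baseline difference of 0.12-0.35 SD would reach significance in only about 9-42% of trials.

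It is also fair to say that the assumptions, not the documents, drive the numerical range.

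**Conclusion.** The point holds and must be fixed. The design as described is quasi-randomized, and the label in section 2.3 is wrong as written. That conclusion rests on the text alone and needs no assumption.

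The size of any resulting bias is unknown. Nothing in the documents shows that steering would occur. Under the assumed inputs the false-positive rate runs from barely above 5% to about 42%, so the figures show what the design leaves open and do not forecast what will happen. They also assume 50 analysed per arm and an unadjusted two-sided 5% test, a level the plan does not state. Selection at entry on unmeasured prognosis cannot be repaired at analysis, which is why it should be dealt with in the design.

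**What to change.** **Preferred.** In section 2.6, replace alternation with a computer-generated list in randomly varying permuted blocks, and state whether there is one list or one per hospital. Have it held by staff who do not enrol patients. Reveal the arm only after consent and, where the visit order allows, after the baseline measures.

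**If alternation is kept.** Delete the word randomized from section 2.3, and describe and report the trial as quasi-randomized. State in section 2.6 whether alternation runs by patient or by date, and per site or overall.

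**Cost.** Either option is a short amendment to sections 2.3 and 2.6. The preferred one also needs a one-off list and someone outside recruitment to hold it; the documents do not name such a person. The number of patients does not change. With blocks of 4 and 6 and 100 patients, simulation gives 50/50 in about 78% of trials and 51/49 in the rest with one list. With three site lists, the arms differ by at most 4 patients in over 99%. Blocks remain partly guessable: someone who sees every past arm would be right about 69% of the time, against 100% under patient-by-patient alternation once the first arm is known.

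The documents do not give the enrolment status. If patients have already been enrolled by alternation, record the date of the change and report the two allocation periods separately.

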3. medical history of pneumonia, feeding tubes
4. patient age and gender, date of completion or cancer treatment, type of chemotherapy and total radiation therapy dosage

Research information to be placed into medical records would include:

1. Outcomes of therapy (including IOPI results/tongue strength)
2. Changes of research outcome measures pertinent to patient clinical care.
3. Type of exercise regimen the participant used.

2.14.1 Will protected health information from a non-UPMC/Pitt HIPAA covered entity be obtained for research purposes or will research data be placed in the non-UPMC/Pitt medical record?

* No

If Yes, describe how the HIPAA requirements will be met:

I, [name] , certify that any member of my research team accessing, reviewing and/or recording information from medical records have completed the CITI Privacy & Information Security course or, if completed within the past year, the Internet-Based Studies in Education and Research (ISER) HIPAA for Researchers (Formerly RPF Module 6). The HIPAA certificates must be available for review if audited but do not need to be uploaded into this OSIRIS application.

* Yes

2.14.2 Are you requesting a waiver of the requirement to obtain written HIPAA authorization for the collection of the PHI?

* No

View: 2.15

Section 2 - Research Design and Methods**2.15 Does this research study involve the long-term storage (banking) of biological specimens?**

* No

2.15.1 Broadly describe the intended future use of the banked biological specimens:**2.15.2 Indicate the planned length of storage of the banked biological specimens:**

*

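### No masked assessor is planned for week-8 tongue pressure or FOIS, and nothing stops the therapist who trained a patient from also assessing that patient

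*Combined protocol and SAP*

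**What the plan says.** - **Who measures at week 8.** Section 2.6 states that "the clinician will repeat the FOIS and weigh the subjects" at the standard-of-care follow-up visit. For tongue pressure it says only "Finally isometric pressure (tongue strength) will be measured at this point", with no role attached. The form's own instruction at 2.6 asks for the personnel, by role, who perform each procedure. Section 2.7 repeats the same description.
- **Who tests and who teaches.** Section 4.13 says "there are 5 Speech Language Pathologists (currently not listed as co-investigators) that will be directly involved in the care of the participants", and that they will be "assisting with the swallowing testing as well as instructing the subjects in the proper therapy techniques and proper use of the IOPI device".
- **Masking.** The design answer in 2.3 is "Randomized, observational, longitudinal, descriptive, crossover". The prompt offers blinding terms and none is used. No other section provides for a masked or independent assessor.
- **Knowledge of the arm.** A clinical investigator makes the assignment (2.6): "This assignment will be in an alternating fashion based on date of enrollment". Section 2.14 lists, among the items to be placed in the medical record, "Type of exercise regimen the participant used".
- **Status of the two measures.** Tongue pressure is item 1 of the main outcomes in 2.17, and FOIS is part of item 4. Section 2.18 plans t-tests, including a between-group comparison at the end of 8 weeks. Its list of measures includes tongue pressure but not FOIS.

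**The concern.** Both measures are taken live and leave room for the assessor to influence the result. FOIS is a clinician's judgement of current oral intake. Tongue pressure is an instrument reading, but it depends on the patient's effort, and so on how the assessor instructs and encourages. Section 2.6 fixes no encouragement standard, number of trials or scoring rule. Unlike the swallow-study video, neither measure can be re-rated later by someone unaware of the arm.

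Staff can know the arm, and section 5.12 states a possible benefit for the IOPI group (faster and enhanced recovery). If an assessor who knows the arm encourages IOPI patients harder, the week-8 difference in tongue pressure contains that extra effort, and the planned t-test cannot separate it from a treatment effect. The stated objective in 1.1 is to determine effectiveness, so a false signal on the first-listed outcome would matter even in a pilot.

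**Working it through.** **Step 1. What the plan fixes and what it leaves open.**

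| Question | Tongue pressure | FOIS |
|---|---|---|
| Assessor at week 8 | not named (2.6) | a clinician, not further specified (2.6, 2.7) |
| Assessor kept separate from the trainer | not stated | not stated |
| Assessor masked | not stated | not stated |
| Main outcome | yes, item 1 (2.17) | yes, within item 4 (2.17) |
| In the t-test list | yes (2.18) | no (2.18) |
| Research-only procedure | yes (2.7) | no, routine care (2.7) |

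Reading 2.6 with 4.13, the same therapist may train and assess one patient. The plan permits this but does not state it. Tongue pressure is the clearer case because its between-group t-test is explicitly planned.

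**Step 2. The plan's own figure.** Section 3.11 gives 50 + 50 = 100, which matches 3.10. Section 3.12 bases this on the referral base and gives no significance level, power, effect size, SD or dropout, so there is no power calculation to reproduce.

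**Step 3. Illustration of what an assessor-induced shift would do.** None of the following assumptions is in the documents: a two-sided 5% level, equal SDs, no true effect, all 50 per arm analysed, and a shift of b SD in one arm. For a two-sample t-test with n per arm:

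- degrees of freedom = 2n − 2
- noncentrality = b / √(2/n)
- false-positive rate = P(|T| > critical value), with T noncentral t

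For n = 50: degrees of freedom 98, √(2/50) = 0.2. For n = 40: degrees of freedom 78, √(2/40) = 0.224.

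| Assumed shift b (SD) | Noncentrality, n = 50 | False positives, n = 50 | False positives, n = 40 |
|---|---|---|---|
| 0 | 0 | 5.0% | 5.0% |
| 0.1 | 0.5 | 7.9% | 7.3% |
| 0.2 | 1.0 | 16.8% | 14.3% |
| 0.3 | 1.5 | 31.8% | 26.3% |

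**Step 4. Scale.** By the normal approximation, the difference detectable with 80% power at 50 per arm is (1.960 + 0.842) × 0.2 = 0.56 SD. A shift of 0.2 to 0.3 SD is 0.2/0.56 = 36% to 0.3/0.56 = 54% of that.

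**The case against.** The strongest objection is that the text supports only an unspecified assessor. Several stronger readings are tempting, and the documents do not support them.

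- **That trainers are stated to assess their own patients.** Section 4.13 does not say which swallowing tests the therapists help with, nor that the trainer measures the same patient. CS15.2 says that each clinic has both physicians and speech language pathologists, so the FOIS rater need not be the trainer. This stands: the plan allows the overlap but does not prescribe it.
- **That other therapists are free to take the measurements.** All five are described as directly involved in participants' care, treatment is spread over Shadyside and Presbyterian/Montefiore, and no staffing per site is given. This stands, so the remedy has to be conditional on staffing.
- **That FOIS bias feeds a planned t-test.** FOIS is not in the 2.18 list, so the illustration above matches no test listed for it.
- **That post-crossover measurements need masking too.** In 2.6 these are specified only for standard-arm patients who agreed to add IOPI, and 2.18 compares them within that group. There is no second arm to protect.

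It can also be said that week 8 is a standard-of-care visit at which standard-arm patients who still need therapy are offered IOPI, so someone there must know the arm. That is true, but it need not be the person measuring, provided the measurements come first. Tongue pressure is a research-only procedure under 2.7, so a different assessor for it changes no standard-of-care step.

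Finally, masking would leave the IOPI arm's 8 weeks of practice on the test device untouched, as well as any expectation effect in the patient-completed EAT-10 and VAS. Both limits are real. They are separate sources of bias and do not remove this one.

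**Conclusion.** The point holds in a limited form. The plan gives no protection against assessor expectation for two live main outcomes, and its staffing description allows one person to train and assess the same patient. The consequence is clearest for tongue pressure, where coaching differences would enter a planned week-8 between-group t-test. For FOIS the route is less clear because its arm comparison is not listed.

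The size of any bias cannot be derived from the documents. The figures of 8%, 17% and 32% rest on assumed shifts of 0.1, 0.2 and 0.3 SD, a two-sided 5% level, 50 analysed per arm and no true effect. With 40 analysed per arm they are 7%, 14% and 26%. A reader might take them as an estimate of what will happen in this trial; they show only how sensitive the comparison would be. The change is worth making because it is cheap, not because bias has been shown.

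**What to change.** Amend 2.6 as follows.

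1. Use the same fixed tongue-pressure instructions and encouragement script, and the same fixed FOIS questions, in both arms at baseline and at week 8. This part does not depend on staffing.
2. Where existing staffing allows, have week-8 tongue pressure and FOIS taken by an existing clinician or therapist who did not train that patient and has not viewed the exercise-regimen entry. Take both measures before the crossover discussion, and ask the patient not to mention the arm.
3. Record who assessed, whether that person trained the patient, and whether they knew the arm.

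No masking is needed for the post-crossover measurements.

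The cost is a short protocol text, a script, a few data fields and some scheduling effort at the week-8 visit. There is no new staff, visit or procedure, and the sample size does not change. Masking will be imperfect because patients may disclose their arm and the regimen is in the record; the log lets the report say how often it failed.
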